9.7.6 Electrocardiogram (ECG) - *amended*

This section was changed in Amendment 3, see Section 15.1.2.33.

A standard 12-lead ECG will be performed locally at the Run-In Visit, Screening Visit, at Visit 1 (Day 1; baseline), at the yearly visits, and again at the PD and EOS Visits (see Table 9–1). If there is any clinical indication, unscheduled 12-lead ECGs can be performed at any point during the study.

In addition, an ECG should be obtained if potassium >6.5 mmol/L.

The interpretation of the tracing must be made locally by a qualified physician.

The date of the recording must be documented on the ECG section of the eCRF. Each ECG tracing should be labeled with the study number, subject number, and date and kept in the source documents at the study site.

Clinically significant abnormalities should be reported as AEs or outcome event as appropriate (e.g. new onset atrial fibrillation) when not already reported in the medical history or in one of the previous recordings and in the event of worsening of previous findings.

9.7.7 Health-related quality of life (HRQoL) questionnaires

HRQoL questionnaires will be completed by the subject at Visit 1 (Day 1; baseline), the yearly visits and at the PD and EOS Visits (see Table 9–1). The following HRQoL

questionnaires will be used: ▪ Kidney Disease Quality of Life (KDQOL-36) and ▪ EuroQol Group 5-dimension, 5-level questionnaire (EQ-5D-5L). A general description of these questionnaires is provided in Section 16.3.

The subject will be instructed to fill in the questionnaires himself / herself before any other procedure of each visit. Subsequently, a member of the site investigator's team will enter the responses into the eCRF.

9.7.8 Planned optional sub-studies

9.7.8.1 Sub-studies

The results of the sub-studies for Study 17530 will not be presented in its main clinical study report (CSR) but will be provided as separate reports.

9.7.8.1.1 Echocardiography sub-study - *amended*

This section was changed in Amendment 3, see Section 15.1.2.34.

At selected centers, approximately 500 subjects per study consenting to participate in Studies 17530 and 16244 will be invited to take part in an echocardiography sub-study. Subjects will be asked to sign a separate informed consent to participate in this sub-study.

Diabetes mellitus, hypertension and dyslipidemia are CV risk factors which contribute to the CVD continuum and potentially results in a sequence of CV events. The development of HF in subjects with DKD is the most common CV complication and imposes significant morbidity and mortality (30, 42). Patients with symptomatic HF_rEF are excluded from the Phase III program of finerenone in DKD. However, before becoming symptomatic, sub-clinical cardiac dysfunction and abnormal leftventricular structure including leftventricular hypertrophy can be demonstrated in the majority of subjects with moderate CKD. Imaging plays a central role in the diagnosis of structural heart disease. Of the various imaging modalities available, for reasons of accuracy, availability, safety and cost, echocardiography is the method of choice in subjects with suspected or the beginnings of structural heart disease.

In all participating sites, echocardiography will be performed according to a study-specific protocol at Visit 1 (Day 1; baseline), at yearly visits and at the end of the study (either at the PD Visit or the EOS Visit). If a baseline assessment is not available or analysable, the subject will not continue to undergo echocardiography assessments due to the inability to perform a comparison against baseline.

Echocardiography examinations, data collection and procedures for central blinded adjudication in the echo core laboratory are given in the Echocardiography Manual. In addition, each time an echocardiography is performed, one blood sample should be drawn to assess the following biomarkers shown in Table 9-5.

Table 9–5 Echocardiography sub-study: biomarkers for evaluation

Biomarker	Mechanism	Rationale for assessing this biomarker
NT-proBNP	myocardial pressure-volume overload	NT-proBNP is typically increased in patients with asymptomatic or symptomatic left ventricular dysfunction and is associated with coronary artery disease and myocardial ischemia.
Galectin-3	(Cardiac) fibroblast / cardiomyocyte stress	Gal-3 is barely detectable in cardiomyocytes but cardiac fibroblasts express high levels of this protein Serum Gal-3 predicts short-, mid- and long-term mortality and HF-associated hospitalization in early and late stage HFpEF and HFrEF
sST2	Myocardial stress	In HF, ST2 mRNA and protein are upregulated and protein becomes detectable in serum. In severe chronic HF, change in serum sST2 independently predicts mortality or transplant.
PIIINP	Tissue remodeling / collagen synthesis	PIIINP is produced and secreted into the circulation upon collagen synthesis Increased baseline PIIINP levels are associated with increased risk of death in CHF patients and decreased in response to spironolactone or eplerenone
OPN	Inflammation / tissue remodelling	OPN mRNA and protein are hardly detectable in healthy myocardium, but becomes detectable upon cardiomyocyte and fibroblast injury.

Abbreviations: CHF = chronic heart failure; CRT = cardiac resynchronization therapy; HFp/rEF = heart failure with preserved/reduced ejection fraction; NT-proBNP = N-terminal pro-peptide of brain natriuretic peptide; OPN = osteopontin; PIIINP = N-terminal pro-peptide of collagen III

Local echocardiography examinations will be performed to capture at least all of the variables listed in [Table 9–6](#). The recordings of echocardiography examinations will be digitally transferred to the vendor / echo core laboratory (ECL) for centralized interpretation and reporting. Echocardiography from videotape will be digitized, and analyses will be performed on an offline analysis workstation. Quantitative measures on all study echocardiographies will be performed by dedicated analysts at the core laboratory, who will be blinded to clinical information and randomized treatment assignment. The echocardiography results will not be provided to sites.

Table 9–6 Echocardiography sub-study: variables for evaluation

Variables	Details
LV structure, systolic function and geometry	
 • Left ventricular ejection fraction (LVEF %) using modified Simpson's biplane method • LV end-diastolic volume (LVEDV, mL), LVED volume index (LVEDVi [=LVEDV/body surface area (BSA)], mL/m²) • LV end-systolic volume (LVESV, mL), LVES volume index (LVESVi [=LVESV/BSA], mL/m²) • LV end-diastolic dimension (LVEDD, cm) and LV end-systolic diameter (LVESD, cm) • LV mass (LVM, g) and LV mass index (LVMI [LVM/BSA], g/m²) • Wall thicknesses, including inter-ventricular septum diameter (IVSd, cm) and LV posterior wall diameter (PWd, cm) in diastole • Relative wall thickness (RWT) defined as $[2 \times \text{PWd}] / \text{LVEDD}$ • LV geometry based on RWT and LVMI (normal, concentric remodelling, concentric hypertrophy or eccentric hypertrophy)
LV diastolic function	
 • Left atrial size (LA diameter, cm; LA area, cm²), LA volume index (LAVi [=LA/BSA], mL/m²) • Early diastolic mitral annular velocity (e', cm/s), using average calculated from: 
 ○ Lateral e' (early diastolic mitral annular relaxation velocity at lateral border of mitral annulus [by Tissue Doppler], cm/s) and ○ Septal e' (early diastolic mitral annular relaxation velocity at septal border of mitral annulus [by Tissue Doppler], cm/s) • E wave (mitral peak early diastolic transmitral flow velocity, m/s) • A wave (mitral peak late diastolic transmitral flow velocity, m/s) • Ratio of E/A • Ratio of E/e' (using lateral e', septal e' and average e') • E-wave deceleration time (EWDT, ms)
Right heart function	
 • Pulmonary artery systolic pressure estimated by pressure gradient of tricuspid valve (PGTV) + estimated right atrial pressure (RAP) 
 ○ PGTV [equivalent to peak RV-to-RA systolic gradient] = $4 \times [\text{tricuspid regurgitation velocity (VTR, m/s)}]^2$ ○ Estimated RAP depends on inferior vena cava diameter (IVCD, mm) and its respiratory collapsibility / change with respiration (end expiratory diameter [EED] - end inspiratory diameter / EED x 100, %) as well as the ratio of systolic to diastolic flow signals in the hepatic veins • Right heart function (using tricuspid annular plane systolic excursion [TAPSE], mm)
Other	
 • Assessment of aortic and mitral valves for stenosis or regurgitation, using color or continuous wave Doppler

9.7.8.1.2 Biomarker sub-study

At selected centers, the first approximately 500 subjects per study who consent to participate in Studies 17530 and 16244 will be invited to take part in a biomarker sub-study. Subject will be asked to sign a separate informed consent to participate in this sub-study.

For participating sites, samples for biomarkers will be drawn at Visit 1 (Day 1; baseline), at Visit 3 (Month 4), at yearly visits and at the end of the study (either at the PD Visit or the EOS Visit). The selected biomarkers studied are the ones believed to be relevant to the pathophysiology of the disease processes of CV and renal disease progression. The biomarkers studied are shown in [Table 9–7](#).

Table 9–7 Biomarker sub-study: variables for evaluation

Biomarker	Mechanism	Rationale for assessing this biomarker
NT-proBNP	Cardiomyocyte pressure-volume overload	NT-proBNP is typically increased in subjects with asymptomatic or symptomatic left ventricular dysfunction and is associated with coronary artery disease and myocardial ischemia.
High sensitivity troponin T (hs-TnT)	Cardiomyocyte injury	Cardiac troponin T is independently associated with cardiovascular events and mortality in patients with CKD. Serum levels of hs-TnT reflect subclinical myocardial injury in ambulatory patients.
Cystatin C		Cystatin C level to have an important association with mortality across the GFR range
Neutrophil Gelatinase-Associated Lipocalin (NGAL)	Renal tubular cells injury	Increased NGAL levels are an indicator of progression of renal damage in CKD patients even after adjustment for eGFR

9.7.8.1.3 Iohexol clearance sub-study - amended

This section was changed in Amendment 3, see Section 15.1.2.35.

At selected centers in Italy, at least 50 subjects per study consenting to participate in Studies 17530 and 16244 will be invited to take part in an iohexol clearance sub-study. Subjects will be asked to sign a separate informed consent to participate in this sub-study.

Subjects who are included in this sub-study will have their GFR directly measured by the iohexol plasma clearance technique (43).

Iohexol plasma clearance will be assessed at Visit 1 (Day 1, baseline), at Visit 3 (Month 4) and thereafter at every other visit (i.e. every 8 months) until the end of the study (either at the PD Visit or the EOS Visit) plus an additional assessment at the PT Visit (recovery). The Iohexol results will not be provided to the sites.

The variables for evaluation in this sub-study are as follows:

– Primary variable:

Chronic GFR slope, i.e. the rate of GFR decline from Visit 3 (Month 4) after randomization to the end of the treatment period.

As previously addressed in the AASK trial, this approach is needed to address the biphasic change in GFR decline that is expected after exposure to the study drug. The GFR slope will be determined separately during the first 4 months following randomization (acute slope) and after 4 months (chronic slope). The acute and chronic phases are differentiated because the study treatment might have acute effects on GFR that may differ from its long term effects on disease progression (44, 45) (an approach approved by the U.S. National Institute of Diabetes and Digestive and Kidney Diseases (46)).

– Exploratory variable:

- Change in GFR from Visit 1 (baseline) and at the PT Visit (recovery)
- Acute GFR changes from baseline to Visit 3 (Month 4)
- Acute GFR changes from the end of the treatment period until the end of the recovery period
- Correlation analyses between short term GFR changes between Visit 1 (baseline) and Visit 3 (Month 4) after randomization, and long term GFR decline (chronic slope).

An ANCOVA model will be fitted to the GFR efficacy variables including the factors treatment group, the stratification factors (type of albuminuria, eGFR category, history of CVD) and the baseline GFR as covariate. Corresponding two-sided 95% confidence intervals will be computed. In addition, correlation analyses between short term GFR changes between Visit 1 (baseline) and Visit 3 (Month 4) after randomization, and long term GFR decline (chronic slope).

9.8 Appropriateness of procedures / measurements

All parameters and their methods of measurement are standard variables / methods in clinical studies and / or clinical practice. They are widely used and generally recognized as reliable, accurate and relevant.

10. Statistical methods and determination of sample size

10.1 General considerations

Statistical analysis will be performed using SAS; the version used will be specified in the statistical analysis plan (SAP).

A log-normal distribution is assumed for serum creatinine and UACR. For all other metric variables, a normal distribution is assumed. The distributional assumptions will be investigated and if necessary, nonparametric methods or transformation of the data will be considered.

All variables will be analyzed by descriptive statistical methods. The number of data available, mean, standard deviation (SDv), minimum, median, and maximum will be calculated for metric data. The geometric mean and SDv will be provided instead of the arithmetic mean and SDv for the variables where lognormal distributions are assumed. Frequency tables will be generated for categorical data.

Baseline values will be defined as the last non-missing measurement before randomization (Visit 1). If the last observation available prior to randomization is the measurement from the Screening Visit, this would be used as the baseline value. This also includes assessments from a local laboratory, in case that prior to randomization, no assessment from the central laboratory is available. Otherwise baseline will be missing. The measurement from the Run-in Visit will not be used as a baseline value. If more than one measurement was planned for a scheduled time point, for example blood pressure measurements and heart rate, the mean value of the last set of measurements per time point prior to randomization will be used as the baseline value.

Only the data provided by the central laboratory will be used for analysis, values from local laboratories will not be used in the statistical analysis and listed only.

In the event of repeated measurements for Pre-treatment Visits and the Visit 1 (Day 1; baseline), the closest measurement prior to randomization will be used for analysis instead of the scheduled measurements. At all visits post-randomization and unless stated otherwise, only the values at scheduled measurements will be used for analysis.

The derived visit '*Any time post baseline*' (applicable for efficacy) will include any measurement after randomization, including unscheduled assessments. For the derived visit '*Any time on treatment*', only assessments up to 30 days after last study drug administration, including unscheduled assessments, will be considered (applicable for efficacy; for safety, assessments within 3 days after last study drug administration will be considered).

Further details on the statistical analyses will be provided in the SAP that will be approved before database release.

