Table 1 Protocol amendment summary of minor changes

Section number and name	Description of change	Brief rationale
10.1 General considerations 10.3.2 Treatment duration, extent of exposure, up-titration status and compliance	Specification of baseline values.	This was added to clarify the handling of subjects who did not immediately start with study drug treatment at randomization, because all analyses follow the intent-to-treat principle.
10.1 General considerations 10.3.3.2 Primary efficacy variable: supportive	For on-treatment efficacy analyses, the time window after last study drug administration is increased from 3 to 30 days.	The time window was increased to better reflect the more protracted nature of the development and diagnosis of clinical outcome events of interest in relation to treatment exposure.

continued

Section number and name	Description of change	Brief rationale
10.3.4	Provision of more precise wording about the type of discontinuation.	Considering the nature of the underlying disease and the long duration of the study, it is the impact of permanent discontinuation of the study drug that is of particular interest.
10.3.4.1 Adverse events	New definition of treatment-emergent AEs.	The definition of TEAEs was specified to account for permitted study drug interruptions (i.e. temporary discontinuations) which may occur over extended periods.
10.3.4.2 Laboratory data	Specification regarding interruption of study treatment.	This was updated to consider treatment interruptions in a similar manner as done for the AE presentation.
10.3.3.5.2 Decrease in eGFR 10.3.4.2 Laboratory data	Deletion of the following analyses: 
 • Absolute value of serum potassium >5.0 mmol/L • Relative decrease from baseline in eGFR of $\geq 25\%$ • Increase from baseline in serum creatinine >0.3 mg/dL and >0.5 mg/dL 	Patients remain on study drug treatment with potassium values up to 5.5 mmol/L. Safety specific information will be obtained by analyzing the remaining thresholds of >5.5 mmol/L (moderate hyperkalemia) and >6.0 mmol/L (severe hyperkalemia) for serum potassium. In this long-term trial relative eGFR decrease from baseline $\geq 25\%$ does not provide clinically relevant information. The same applies to analyses of change in serum creatinine, which is already incorporated in the currently planned analyses of change in eGFR.

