10.3.3.2 Primary efficacy variable: supportive analyses

The primary analysis of the primary efficacy variable will be repeated in the PPS as a supportive analysis. Further supportive analyses of the primary efficacy variable will be performed in the FAS and PPS.

The absolute and relative frequency of subjects with an event of the primary composite endpoint until 6, 12, 18, 24, 30 and 36 months will be displayed overall and by treatment group. The number of individual events of the primary composite endpoint until 6, 12, 18, 24, 30 and 36 months will be displayed overall and by treatment group. Frequencies will be calculated for the number of individual events of the primary composite endpoint per subject until 6, 12, 18, 24, 30 and 36 months overall and by treatment group.

Kaplan-Meier estimates (the 25th, 50th and 75th percentile) of the time to the first event of the primary composite endpoint (including 95% confidence interval), overall ‘*survival*’ rates at 6, 12, 18, 24, 30 and 36 months and Kaplan-Meier curves will be presented for each treatment group. These analyses will be presented in total and for each level of the stratification factors (type of albuminuria, region, eGFR category, history of CVD).

The censoring mechanism of subjects without an event of the primary composite endpoint at the time of analysis is assumed to be non-informative for the primary efficacy analysis. Sensitivity analyses will be performed, assessing the impact of potential informative censoring of such subjects. These will include the use of different imputation rules for considering subjects without an event of the primary composite endpoint as having an event or being censored, and will be further outlined in the SAP.

For the individual events of the primary composite endpoint, the number of events per patient-year will be presented overall and by treatment group. The frequency of events per patient-year for a treatment group will be calculated as the number of events observed for a treatment group (counting all events, not only the first one) divided by the sum of the days from first intake of study drug for all subjects within a treatment group and multiplied by 365.25.

An ‘*on-treatment*’ analysis will be performed, including only events occurring while taking study drug or until 30 days after stop of study drug. This analysis will be performed in the FAS.

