6.2.1.2 Primary efficacy variable: supportive analysis

The primary analysis of the primary efficacy variable will be repeated in the PPS as a supportive analysis. For the PPS analysis, the censoring rules for the primary analysis specified in Section 6.2.1.1 will be further restricted to events occurring up to 30 days after last study drug intake.

Accordingly, subjects with censoring or event date more than 30 days after last study drug intake in the primary analysis will be censored at the date of last study drug intake +30 days.

The following supportive analyses of the primary efficacy variable will be performed in the FAS and PPS unless specified otherwise.

The originally planned presentation of absolute and relative frequency of subjects with an event of the primary composite endpoint will be superseded by the Kaplan-Meier estimates described below.

Cumulative incidence probabilities for each treatment group based on Kaplan-Meier estimates for the time to the first primary composite endpoint event and their differences between finerenone and placebo will be derived at appropriate time points along with 95% confidence

intervals (CIs) and Number Needed to Treat (NNT). The CIs will be calculated based on a normal approximation and using the Greenwood formula for the standard deviation [4], and the NNT will be calculated as the inverse difference of the Kaplan-Meier estimates between finerenone and placebo for the selected time points. In addition, corresponding Kaplan-Meier curves showing cumulative incidence probabilities will be presented for each treatment group. These analyses will be presented in total and for each level of the stratification factors.

For the primary composite endpoint and the individual events, the incidence rate per 100 patient-years will be presented by treatment group, which is defined as the number of subjects with an event divided by the time a patient is at risk for the respective event, i.e. either the time from randomization until the first event or the censoring time, multiplied by 365.25*100. Kaplan-Meier plots, logrank tests and Cox proportional hazards regression for the time to first event of the individual components will also be provided as part of exploratory efficacy (see section 6.2.3).

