An ‘on-treatment’ analysis will also be performed, repeating the Kaplan Meier estimates and curves as well as the inferential statistics (stratified logrank test and stratified Cox regression model) on the FAS. For the on-treatment analysis, as described for the PPS analysis above, the censoring rules for the primary analysis will be adapted by further restricting to events occurring up to 30 days after last study drug intake.

The logrank test as well as the Cox regression model will also be performed without including stratification factors. The plausibility of the proportional hazards assumption will be assessed by visually examining the plot of the log of the negative log of Kaplan-Meier estimates of the survival function versus log time for evidence of non-parallelism, and by including a treatment by log-transformed time interaction into the Cox model. For the latter, the SAS code is adapted as follows:

```
PROC PHREG DATA = <dataset>;
  MODEL ttevalue * ttecnsr(1) = trtgrpnr trtltime / RL
  TIES=EFRON ALPHA=0.05;
  STRATA {stratum};
  trtltime = trtgrpnr*log(ttevalue);
RUN;
```

The significance of the interaction will be tested at the 5% type I error level. If the interaction is significant and there is strong evidence of non-proportionality from the plots, time-dependent hazard ratios will be estimated with the model that includes the interaction term.

The censoring mechanism of subjects without an event of the primary composite endpoint at the time of analysis is assumed to be non-informative for the primary efficacy analysis. This also implies that the primary analysis is valid under a missing at random (MAR) assumption. Sensitivity analyses will be performed, assessing the impact of a potential informative censoring of subjects lost to follow-up or with withdrawn consent. Non-CV deaths will be treated as censored observations as in the primary analysis.

A summary of the amount of missing data by treatment arm will be given, including number of subjects who have incomplete follow-up on the respective endpoint as well as the ratio of the observed follow-up time to the expected follow-up time for the respective endpoint.

Robustness with respect to missing data will be investigated with a tipping point analysis on the FAS (based on the ITT approach). The analysis will:

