- Number of subjects discontinuing study drug permanently due to worsening of renal function

These will be summarized by treatment group using frequency counts. For the number of subjects with these events, the summary will be provided once for all events and once for all treatment-emergent events.

Cumulative incidences based on Aalen-Johansen estimates (including 95% confidence intervals) [14] and accounting for mortality as competing risk will be provided for the time to first treatment-emergent hyperkalemia event (any, leading to hospitalization and leading to permanent discontinuation of study drug). For this analysis, the person-time at risk for a single subject is the number of days from first intake of study drug until the event of interest or until the minimum of (date of death, last exposure to treatment +3 days) excluding temporary study drug interruptions (i.e. the time between start of a temporary study drug interruption + 3 days until the end of the interruption).

Furthermore, concomitant medications taken as treatment for treatment-emergent hyperkalemia will be shown by treatment group and overall.

Separate tables summarizing TEAEs, study drug-related TEAEs, and SAEs that occurred in more than 5% of the subjects will be provided.

Deaths, SAEs and AEs leading to permanent study drug discontinuation will be listed separately.

In addition, subjects with a COVID-19 adverse event will be summarized and listed. The number of subjects affected by the COVID-19 pandemic and experiencing treatment-emergent adverse events since the country-specific COVID-19 onset date will also be summarized, along with a listing of all adverse events since the country-specific COVID-19 onset date of subjects with a COVID-19 infection.

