7.4 Overview of Changes to SAP – from version 4.0 to version 5.0

Major changes compared to version 4.0:

- Addition of section 4.8 “Considerations with regard to the COVID-19 pandemic” and section 6.2.4 “Supportive efficacy analyses related to the COVID-19 pandemic” as well as descriptive analyses throughout sections 6.1 (Population characteristics) and 6.4.1 (Adverse events) to evaluate the impact of COVID-19

- Addition of subgroup analyses for any treatment-emergent hyperkalemia and addition of new subgroup factors mainly for safety (section 4.5.4)
- Removal of redundant medical history items (section 6.1.3)
- Addition of new concomitant medication of interest “Trimethoprim and derivatives” and extension of list of concomitant medications of interest included in shift table for baseline vs. post-baseline use (section 6.1.4)
- Modification of overall titration status table to also include number of subjects up-titrated at least once and down-titrated at least once and addition of new table for number of subjects on 10 mg, 20 mg and on an interruption of study drug at specific time points (6.1.5)
- Clarification of Kaplan-Meier summaries and curves to present cumulative incidence probabilities and to include calculation of NNTs (section 6.2.1.2)
- Extension of the FAS on-treatment analysis to all secondary efficacy variables and to also include Kaplan Meier summaries and curves (sections 6.2.1.2 and 6.2.2.2)
- Modification of description for table on missing data for endpoint follow-up to also include ratio of observed to expected follow-up time (section 6.2.1.2)
- Addition of exploratory efficacy endpoints: Time to stroke, time to myocardial infarction, time to first occurrence of the composite endpoint of CV death, hospitalization for HF or non-fatal myocardial infarction, and time to first occurrence of the composite endpoint of CV death for HF or HF hospitalization (section 6.2.3)
- Clarification of wording for definition of shifts in albuminuria shift table (section 6.2.3.2)
- Modification of correlation analysis for acute vs. chronic eGFR slopes to be repeated by treatment group (section 6.2.3.3)
- Addition of new table for concomitant medications taken as treatment for treatment-emergent hyperkalemia (6.4.1)
- Clarification of technical details for missing data imputation for UACR at Month 4 in Appendix B (section 9.2)

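### On-treatment efficacy follow-up runs to 30 days after the last dose, so time beyond day 30 of an interruption counts only for patients who survive and restart

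*Protocol*

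**What the plan says.** The rule that governs events is in SAP 6.2.1.2. For the FAS on-treatment analysis the primary censoring rules are "adapted by further restricting to events occurring up to 30 days after last study drug intake". The censoring is spelled out in the per-protocol paragraph of the same section, to which the on-treatment text refers: "subjects with censoring or event date more than 30 days after last study drug intake in the primary analysis will be censored" at last intake plus 30 days. SAP 6.2.2.2 carries the supportive analyses over to the secondary time-to-event endpoints, and SAP 7.4 records the "Extension of the FAS on-treatment analysis to all secondary efficacy variables". All-cause mortality is one of these. CV death enters as the fatal part of the primary composite.

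Protocol 10.1 uses the same anchor for assessments ("only assessments up to 30 days after last study drug administration, including unscheduled assessments, will be considered"), and SAP 6.2.3.2 and 6.2.3.3 use it for the on-treatment UACR and eGFR models. Protocol 10.3.3.2 words the event analysis differently, as "including only events occurring while taking study drug or until 30 days after stop of study drug". It does not say whether a temporary stop counts.

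The safety rules do deal with interruptions. Amendment 4 changed the treatment-emergent definition because of "permitted study drug interruptions (i.e. temporary discontinuations) which may occur over extended periods". SAP 6.4.1 ends the adverse-event window 3 days after a stop of either kind and computes hyperkalemia person-time "excluding temporary study drug interruptions". One efficacy table, the COVID-19 summary in SAP 6.2.4, also counts 30 days from any temporary or permanent stop.

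**The concern.** The date of last intake is known only in retrospect. Take two patients who both stop drug on the same day. One restarts after five months, so last intake lies later and the whole gap counts as on-treatment time. The other dies in month four of the gap. Last intake is then the day the gap began, follow-up is cut 30 days later, and the death is dropped. Beyond day 30, gap time is kept for survivors who restart and removed for those who die, so it is free of deaths by construction.

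If interruption were equal in the two arms, both mortality rates would be too low but their ratio would be unaffected. If one arm has more long interruptions, its on-treatment mortality is lowered more. Protocol 9.7.1 withholds study drug at potassium above 5.5 mmol/L and names hyperkalemia as a main risk of this drug class, finerenone included, so finerenone is the plausible arm. An on-treatment mortality result will be read as support for the primary result, and this distortion does not shrink with more patients.

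**Working it through.** **Inputs from the documents.** The window is last intake plus 30 days (SAP 6.2.1.2), so w = 30/365.25 = 0.0821 years. Permanent finerenone discontinuation is 5% per year (Protocol 10.4), used here for both arms as s = 0.05. The plan gives no figure for interruptions. Its event target of 970 to 976 does not involve this rule; a log-rank calculation with the Protocol 10.4 inputs returns 972 and 979 events, so that figure reproduces and is not in question.

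**Assumptions.** Death hazard h = 0.03 per year in both arms, on and off drug, so the true ratio is 1.00. Interruptions start at rate a per on-drug year, and gap lengths are exponential with mean m days. A death rate of 0.02 gives almost the same ratios.

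**Formula.** Let r = 365.25/m, k = r + h and q = 1 − exp(−kw). Per on-drug year:

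- Time counted if the window closes 30 days after any stop: T_any = 1 + a·q/k + s(1 − exp(−hw))/h.
- Extra time that the last-intake rule adds: T_last − T_any = a·(r/k)·(1 − q)/k. This is the post-day-30 gap time of patients who restart.
- Both rules count the same deaths, so the recorded rate under the last-intake rule is h(1 − g), with g = (T_last − T_any)/T_last. The recorded ratio is (1 − gF)/(1 − gP), for finerenone (F) and placebo (P).

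**Worked case: 0.20 versus 0.10 per year, mean gap 90 days.** r = 4.058, k = 4.088, q = 0.285.

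- Finerenone: T_any = 1 + 0.2 × 0.285/4.088 + 0.0041 = 1.0181. Extra time = 0.2 × 0.9927 × 0.7148/4.088 = 0.0347. gF = 0.0347/1.0528 = 0.0330, rate 2.90 per 100 patient-years.
- Placebo: T_any = 1.0111, extra time 0.0174, gP = 0.0174/1.0284 = 0.0169, rate 2.95.
- Ratio = 0.9670/0.9831 = 0.984. With the window closed at any stop, both rates are 3.00 and the ratio is 1.000.

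**Range.** The closed form assumes unlimited follow-up. With finite follow-up, gaps still open at the end are cut at day 30, so the effect is smaller. The last column is a simulation with 3.4 years of follow-up (assumed); repeat runs differ by up to 0.01.

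| Interruptions per year, F vs P | Mean gap | Closed form | Simulation |
|---|---|---|---|
| 0.20 vs 0.10 | 30 days | 0.997 | 0.996 |
| 0.20 vs 0.10 | 60 days | 0.991 | 0.993 |
| 0.20 vs 0.10 | 4 months | 0.98 | 0.98 |
| 0.20 vs 0.10 | 8 months | 0.95 | 0.97 |
| 0.30 vs 0.10 | 6 months | 0.93 | 0.95 |

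At 0.30 versus 0.10 and 60 days the closed form gives gF = 0.028, gP = 0.0096 and a ratio of 0.972/0.9904 = 0.98. Closing the window at any stop gives 1.00 in every row, within simulation error. Equal interruption (0.20 in both arms, 180 days) leaves the ratio at 1.00, but both rates read 2.78 instead of 3.00.

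**If the death hazard triples during an interruption** (closed form):

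| F vs P, mean gap | Last-intake rule | Any-stop rule |
|---|---|---|
| 0.20 vs 0.10, 90 days | 0.997 | 1.013 |
| 0.20 vs 0.10, 180 days | 0.980 | 1.014 |
| 0.30 vs 0.10, 180 days | 0.961 | 1.029 |

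**Per-protocol set.** SAP 5.3 removes compliance below 80%, and SAP 6.1.5 counts every day from randomization to last intake as planned, gaps included. Over 3.4 years (1,242 days), a restarted gap longer than 0.20 × 1,242 = 248 days fails that limit even with perfect intake otherwise. Applying the exclusion to the three simulated cases with gaps of 4, 8 and 6 months gives ratios of about 0.99, 1.01 and 1.01.

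**The case against.** The strongest objection is size. The reason for expecting more interruption on finerenone is potassium, and Protocol 9.7.1 calls for a re-check within 72 hours and a restart once potassium has fallen. SAP section 3 asks for re-introduction as soon as medically justified. Only time beyond day 30 matters, and with gaps averaging two months or less the effect is 1% or less at 0.1 versus 0.2 per year. This stands. Amendment 4 shows that long gaps are foreseen, not that they differ by arm.

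The remedy is also not free of bias. Patients may interrupt because they are ill, and leaving the risk set is then informative. In one tripled-hazard case the present rule lands nearer to 1.00 (0.997 against 1.013), because two biases offset each other. That stands too, but the present rule still classifies time by what happens later.

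An imbalance would be partly visible, since SAP 6.1.5 tabulates interruptions by arm. Those tables would prompt the question but would not correct the mortality estimate.

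A reader might infer that the per-protocol results are likewise tilted towards finerenone, since they share the 30-day rule. The documents do not support that: the compliance exclusion removes many of the patients who restart after long gaps, and the direction is undetermined. Nor do they support reading the Protocol 10.1 sentence as the rule that censors deaths. It concerns assessments; the event rule is in the SAP.

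**Conclusion.** The point holds for the FAS on-treatment time-to-event analyses. Gap time beyond day 30 cannot contain a death, so on-treatment mortality is understated, more in the arm with more long interruptions. Under no true effect the recorded mortality ratio is about 0.99 or closer to 1 for mean gaps of one to two months (0.98 in the closed form if finerenone interruption reaches 0.3 per year at 60 days), and about 0.95 to 0.98 for mean gaps of four to eight months over 3.4 years. These sizes rest wholly on assumed interruption rates and lengths. That finerenone is the affected arm is plausible, not stated.

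The effect on the primary composite is smaller, because a non-fatal event during a gap still counts if the patient restarts. The on-treatment UACR and eGFR models include values taken well into a gap, but no direction is claimed for them; off-drug UACR values would more plausibly dilute an effect.

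It would be tempting to conclude that the trial's main result is biased. It is not touched: the primary and secondary analyses use the FAS and count events regardless of interruption, and the on-treatment analyses are supportive and carry no alpha. The event target is unchanged.

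**What to change.** In SAP 6.2.1.2 and 6.2.2.2, define efficacy on-treatment time from the exposure records as each intake period plus 30 days. A subject leaves the risk set 30 days after any temporary or permanent stop and re-enters at restart, using counting-process forms of the Cox model and log-rank test. This matches the COVID-19 table in SAP 6.2.4 and fits the wording of Protocol 10.3.3.2. Use the same window in the on-treatment UACR and eGFR models (SAP 6.2.3.2, 6.2.3.3) and for the derived visit in Protocol 10.1. At minimum, report this version beside the last-intake version, with the share of on-treatment time lying beyond day 30 of interruptions in each arm.

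The cost is SAP wording and some programming. Interruptions and restarts are already recorded in the eCRF, and SAP 6.1.5 already derives interruption status over time. Slightly fewer events will be counted. The report should say that leaving the risk set at an interruption may itself be informative: with no drug effect the ratio is 1.00 only if the death hazard is the same on and off drug, and about 1.01 to 1.03 if it triples off drug.
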